Postural stability declines with aging (2). Previous studies have shown that dance interventions in many genres have had positive effects on postural stability in older adults, including genres such as contemporary dance (2), Argentine tango (3), traditional Greek dance (4), Pilates (5), and Latin dance (5). Kattenstroth suggests that a special dance program designed for older adults may lead to improvements in postural stability following the intervention (6). Ferrufino et al compared the effectiveness of a contemporary dance intervention with that of a fall prevention program and found that the dance intervention was more successful in improving postural stability (2). Additionally, Zhang et al found that older adults who dance also tend to have better postural stability than non-dancers (7), while Dewhurst et al found that older dancers have a reduced amount of regulatory activity needed to maintain postural stability (8). While studies have been conducted to examine postural stability in professional ballet dancers (9,10), few have examined the effects of a beginning ballet class for older adults on postural stability.

While the use of force plates for balance research is the gold standard, the use of Wii balance board alongside specialized balance software is a more affordable option which has surprisingly high reliability and validity for use in scientific research (11-13). As the early data from the Bridges to Skidmore research (IRB #1610-557) has demonstrated positive changes in balance following participation in dance, the use of Wii balance boards to more deeply understand the changes in balance in older adults appears to be an appropriate progression for this work.

Thus, the purpose of this current study is to examine the changes in postural stability in older adults following exposure to a beginning ballet dance technique course. It is hypothesized that a significantly reduced body sway will be observed in participants following a ballet dance training course over a 10-week period.

10. Human Participants:

A. Who are the participants?

Participants will be people ages 55 and up who agree to participate in a 10-12-week beginning ballet class program. Participants must be independent with activities of daily living (ADLs), require no walking aides, and be free from cardiovascular or neurological disease (5, 14-15).

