Exclusion criteria will be active participation in a physical therapy program with the goal of improving functional mobility, missing six or more of the ballet classes offered during the 10-week period, receiving dance training in the past, not being independent with ADLs, using a walking aide, or diagnosis of cardiovascular or neurological disease. However, participants will not be excluded if they have a pacemaker if they are also cleared by a physician as a 'no restrictions' status for physical activity as indicated by the required intake form. Additionally, we will recruit a control group of adults ages 55 and up that will not participate in the dance class. As with the experimental group, control group participants must be independent with ADLs, require no walking aides, and be free from cardiovascular or neurological disease. Exclusion criteria for the control group will be participation in a physical therapy program with the goal of improving functional mobility, receiving dance training in the past, not being independent with ADLs, using a walking aide, or diagnosis of cardiovascular or neurological disease. The control and treatment groups are determined by the individuals themselves based on their desire to participate in the ballet classes.

B. How many participants do you plan to have in your study?

Each semester, we aim to recruit a convenience sample of up to 20 people for the control group and 20 people for the experimental group. We will cap the class at 20 each semester to assure a safe and appropriate ratio of students in the classroom. We aim to have one Skidmore dance student act as the lead teacher and be present at every ballet class, at least 1-2 additional Skidmore students assistant-teaching each class, and up to 20 individuals participating in the dance classes. Participants will be

responsible for finding transportation to campus and will be greeted by at least one participating Skidmore students at Dance Center entrance.

Participants may opt to leave the ballet classes and the study at any time. Participants who opt to withdraw from the study will not be asked to participate in the postural stability post-testing procedures.

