Participants in the experimental group may choose to enroll in the beginning ballet class for more than one semester, though they are not required to. If they do, their participation number will remain constant throughout every semester of their participation in order to track changes in postural stability over longer periods of time. Every semester that a participant enrolls in the study, their postural stability will be assessed at the beginning and end of the semester just as for first-time experimental group participants. Additionally, control group participants may decide to join the experimental group at the beginning of a semester. However, experimental group participants may never participate in the control group in a later semester as they would meet exclusion criteria of prior dance training for that group.

C. How will the participants be contacted or recruited?

The PI will contact activities directors at senior centers and independent living communities in Saratoga Springs to inquire about having the ballet classes listed as activities with the PI's contact information so that interested parties may register for the class and receive more information about the corresponding research procedures. If granted permission, posters will also be put at these senior centers and independent living communities. Additionally, posters will be hung around Skidmore's campus to encourage participation, again with the PI's contact information so interested parties may register for the class and receive more information.

The control group will consist of people ages 55 and up who are not interested in taking a dance class but are willing to participate in the outcome measures of this study. As with the experimental group, the control group will be invited to participate by activities directors at senior centers and independent living communities and through self-nomination in response to posters hung in various locations. To participate, individuals will contact PI [name] via email to get more information and to register for the class. Any emails from the researchers to individuals encouraging them to participate, and prior to pre-and post-testing sessions, will include the following:

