Both the pre and post data collection will take approximately 15 minutes per participant at each testing session. Participants will receive instructions prior to each trial of 30 seconds with at least one research assistant spotting the participant should they lose their balance. Participants will be asked to stay in a static standing position for 3 trials of 30 seconds while standing on a Wii board in four of the following conditions : 1) bilateral stance with eyes open, 2) bilateral stance with eyes closed, 3) unilateral stance on the right limb 4) unilateral stance on the left limb. Participants will be given a 15 seconds rest period between each trial and will be told they may stop and rest at any moment during the testing process.

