11.3 Data Analysis

Five measures of postural stability were examined in this study: the area the CoP traveled through during each 30-second trial, the CoP displacement in the x- and y-planes during each trial, and the absolute value of the average speed of the CoP in the x- and y-planes through each trial. Non-parametric Wilcoxon signed ranks tests were used to compare these values at baseline and post-testing within each group, while non-parametric Mann Whitney U tests were used to compare the delta (post minus pre) values between groups for EO and EC trials.

12. Consent:

Participants will sign an Informed Consent must prior to beginning of any testing. Please see attached informed consent for details.

13. Risks and Debriefing:

The postural stability data collection offers minimal risk to participants. Fatigue and falls have been shown to be minimal in prior research (see background information on postural stability references) in older adults. To ensure no risk to participants, participants will repeatedly be reminded they may rest or stop at any moment, without penalty of any kind. As well, one 'spotter' will be present during all data collection trials to assist participants should they lose their balance.

The dance movements performed in the intervention sessions carry a minimal risk of injury. Ballet movements presented in the class will likely be outside of typical movement patterns and therefore hold some inherent risk, including slips, falls and muscle strains and sprains. To combat the likelihood of injury during the class, participants will be thoroughly instructed on the movement, technique, and expectations for each combination. The ballet class will be gentle with little to no aerobic activities, making this appropriate for all participants meeting our inclusion criteria. Additionally, while the class will be primarily instructed by the lead teacher, additional Skidmore students will be present to help decrease the risk of injury during the dance class. This way, each participant has additional support throughout the class time as needed.

If a serious injury occurs, the Skidmore Campus Safety will be called and/or 911 depending on the severity of the injury. If an injury occurs during testing off-campus, 911 will be called to appropriately treat the participant for any injury sustained.

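### One directional sway hypothesis is tied to no measure, stance condition or contrast, while Section 11.3 supplies ten between-group and at least 20 within-group tests with no primary comparison, significance level or correction in the text available

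*Combined protocol and SAP*

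**What the plan says.** The background section, just before Section 10, states one hypothesis: "a significantly reduced body sway will be observed in participants following a ballet dance training course over a 10-week period". It is directional and worded as a change in the ballet participants. It names no sway measure, stance condition or comparator.

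Section 11.3 opens: "Five measures of postural stability were examined in this study: the area the CoP traveled through during each 30-second trial". The other four measures are CoP displacement and absolute average speed, each in the x and y directions. No order of importance is given. Two sets of tests follow:

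- Within groups: "Non-parametric Wilcoxon signed ranks tests were used to compare these values at baseline and post-testing within each group".
- Between groups: "non-parametric Mann Whitney U tests were used to compare the delta (post minus pre) values between groups for EO and EC trials".

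Section 11.2 describes the measurements behind these tests: "Participants will be asked to stay in a static standing position for 3 trials of 30 seconds while standing on a Wii board", in four stance conditions. It gives no rule for reducing the three trials to one value.

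On timing, Section 10.B says: "Each semester, we aim to recruit a convenience sample of up to 20 people for the control group", with the same number for the ballet group. It also says: "Participants in the experimental group may choose to enroll in the beginning ballet class for more than one semester", and it lets controls move to the ballet group in a later semester. Section 14 allows the de-identified database to be passed on for analysis and foresees that, after Spring 2019, later databases may go to other students for the same purpose. No analysis point is stated.

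One part of the document was not available for review. The text that was available contains no primary comparison, significance level, test order or multiplicity correction.

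**The concern.** A hypothesis of significance needs a stated result that would confirm it. Here four choices are open: the measure, the stance condition, the contrast (pre-post change in the ballet group, or difference in change between groups), and the semester after which the test is run. The trial rule is a fifth.

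The contrast matters most for interpretation. The hypothesis reads as a pre-post change, so a significant Wilcoxon result in the ballet group could be offered as support even with no difference from controls. That result does not test ballet against no ballet.

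If the deciding result may be picked after the results are known, a claim of significantly reduced sway carries an unknown false-positive rate, above that of a single test.

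**Working it through.** **1. Count of tests.**
- Between groups: 5 measures × 2 conditions = 10, if eyes open and eyes closed are tested separately and the three trials give one value.
- Within groups: 5 measures × 2 groups × 2 conditions = 20, or 5 × 2 × 4 = 40 if the one-leg stances are included.
- Ballet group alone: 10 of those 20.

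**2. Assumptions.** The available text gives no significance level or power, so there is no planned figure to reproduce. I assume two-sided 0.05 per test (0.025 in the direction of reduced sway), no true effect, one record per participant, and that any one significant between-group result counts as support. The plan neither states nor excludes that last rule.

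**3. Independent tests.**
- Reduced-sway direction: 1 − 0.975^10 = 0.224.
- Either direction: 1 − 0.95^10 = 0.401.

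**4. Correlated tests.** The measures come from the same trials and are probably correlated, but the documents give no correlation. With k equally correlated normal statistics (correlation ρ), the chance of at least one false result in the reduced-sway direction is 1 − ∫ φ(u) · Φ((1.96 − √ρ·u)/√(1−ρ))^k du. The either-direction column uses the matching two-sided integral.

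| ρ | 10 tests, reduced sway | Same, simulated Mann-Whitney, 20 per group | 6 tests, reduced sway | 10 tests, either direction |
|---|---|---|---|---|
| 0 | 22.4% | 22.0% | 14.1% | 40.1% |
| 0.5 | 14.4% | 14.7% | 10.4% | 28.7% |
| 0.8 | 8.6% | 9.3% | 6.9% | 17.3% |
| 0.9 | 6.4% | 6.6% | 5.4% | 12.8% |
| 0.95 | 5.0% | 5.4% | 4.4% | 10.0% |
| one test | 2.5% | | 2.5% | 5% |

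The simulation used 20,000 replicates. The six-test column covers the case where displacement and speed are both path length over a fixed 30 s. Speed then adds nothing, and 3 measures × 2 conditions = 6 tests are distinct. If the hypothesis is read as pre-post change in the ballet group, its ten Wilcoxon tests give nearly the same figures as the ten-test column (within about 1 point at 20 participants).

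**5. Error rate under the two remedies (independent tests).**
- One primary test, with the others tested only after it succeeds: 0.05 in either direction, 0.025 for reduced sway.
- Holm over all ten: 1 − 0.995^10 = 0.049 in either direction, 1 − 0.9975^10 = 0.025 for reduced sway.

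**6. Power cost of Holm over ten.** Assume 20 per group and a difference of 0.8 SD, by the normal approximation. The standardised effect is 0.8 × √(20/2) = 2.53.
- At 0.05: Φ(2.53 − 1.96) = 0.72.
- At Holm's first step, 0.05/10 = 0.005: Φ(2.53 − 2.81) = 0.39.

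**The case against.** The best case for the plan has four parts.

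- **The choice is narrower than it looks.** Section 11.3 fixes the five measures, the tests, the change score and, for the between-group tests, the two conditions. If all ten results are reported, a reader can adjust for multiplicity. This is fair, but it does not say which result confirms the hypothesis, and it leaves the contrast, the trial rule and the timing open.
- **The inflation may be small.** With six distinct tests and correlation 0.9 to 0.95, the rate is about 4% to 5% against 2.5%. This stands, and the documents cannot say where in the range the truth lies.
- **The study is small and exploratory.** The available text does not call the analysis exploratory, and the hypothesis is one of significance. The label would be an acceptable remedy if it were adopted.
- **Self-selection is the larger problem.** Section 10.A says: "The control and treatment groups are determined by the individuals themselves based on their desire to participate in the ballet classes". A corrected p-value would still not isolate an effect of ballet. This also stands, but it is a separate problem.

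Three stronger readings are tempting and not supported. A reader might infer that the ten Mann-Whitney tests are the stated test of the hypothesis, but the documents make no such link. A reader might take the past tense of Section 11.3 as a sign that results were picked. It shows only that some data may already have been analysed. A reader might also quote 40% as the error rate. That figure needs independent tests and counts results showing worse sway, which would not support the hypothesis.

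**Conclusion.** The point holds on the available text. The plan states one directional hypothesis and does not fix the measure, condition, contrast or analysis time that decides it. It provides ten between-group and at least 20 within-group tests, with no significance level or correction.

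Under the assumptions in the working, the chance of a false reduced-sway finding among the ten between-group tests is about 5% to 22%, against 2.5% for one test. If only six tests are distinct, it is about 4% to 14%. The range is illustrative. It rests on equal correlation across tests and on any one result counting. It leaves out the within-group tests, repeated analysis over semesters and repeat enrolment.

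The change is worth making because it is cheap. The finding describes what the plan permits and is not evidence of selective reporting.

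**What to change.** For data not yet analysed, choose one option in advance.

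**Option A, one primary test.** Name one measure, one condition and the rule for combining the three trials (the investigators' choice). Make that the primary between-group Mann-Whitney comparison of change at two-sided 0.05. Reword the hypothesis as a greater reduction in sway, that is a more negative post-minus-pre value, in the ballet group than in controls. Only this test can support the hypothesis. Test the other nine with Holm (first step 0.05/9 = 0.0056) only if the primary is significant in the direction of reduced sway. Otherwise report them as exploratory.

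**Option B, no primary.** Apply Holm to all ten between-group tests. Only Holm-significant results in the reduced-sway direction support the hypothesis. The trial rule is needed here too, since the count of ten depends on it.

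**Under either option:**
- treat the within-group tests as descriptive;
- use one record per participant, the first enrolment, in the confirmatory test;
- state the one time point at which that test is run;
- exclude semesters already analysed from it and label their results exploratory.

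If neither option is adopted, declare all sway analyses exploratory and report estimates with confidence intervals.

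**Cost.** Wording, and relabelling of any results already produced. Option A leaves no fallback measure if the primary fails. Option B starts at 0.005 per test, with power for a given measure falling from about 72% to 39% under the assumptions in the working. Neither option removes bias from self-selected groups.

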11.2 Data Collection

Data collection will take place at the dance conference room (Williamson Sports Center), the Human Performance Teaching Lab (Sports 101, Williamson Sports Center), multipurpose room (Williamson Sports Center), the intramural gym (Williamson Sports Center), or at the Prestwick Chase facility or the Saratoga Senior Center (if requested by an activities director) prior to the start of the ballet classes each semester with post-testing to be completed the week of, or following, the final ballet class of the semester. Tests of postural stability will be verbally explained/instructed to create clear expectations for the test and to help decrease any fear or anxiety surrounding the process.

Data collection will be conducted by [name] '19 with help from [name] as needed. Following the Spring 2019 semester, [name] will lead data collection and/or find another Skidmore student to help with data collection who is trained with this protocol. [name]

[name] will be contacted as needed to ensure the proper functioning of the data collection system/protocol. [name] has already received training in the data collection procedure from [name] and [name] from a prior research investigation examining postural stability in novice collegiate dancers (IRB 1712-683). Once calibrated, the use of balance boards to collect data on postural stability requires very little technical skill, and therefore it is appropriate for a trained student researcher to lead this process. Any additional student data collectors present will only be there to assist and guard the participants from falling. Student data collectors will be trained in all procedures and techniques directly by the PI or supervising faculty members prior to any data collection and must be able to demonstrate competency in testing prior to administering any tests on participants.

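### Could the two CoP speed outcomes measure start-to-end shift instead of sway, since section 11.3 gives no formula?

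*Combined protocol and SAP*

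**What the plan says.** Section 11.3 is the only place where the outcomes are defined. It opens with "Five measures of postural stability were examined in this study". One is the area covered by the CoP. Two are displacements, given as "the CoP displacement in the x- and y-planes during each trial". The remaining two are speeds, which the section words as "the absolute value of the average speed of the CoP in the x- and y-planes through each trial". It gives no formula, sampling rate, filter or software definition.

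The between-group analysis uses Mann-Whitney tests to "compare the delta (post minus pre) values between groups for EO and EC trials"; EO and EC are eyes open and eyes closed. Wilcoxon signed-rank tests compare baseline with post-testing within each group. The hypothesis, in the background text before item 10, is that "a significantly reduced body sway will be observed in participants following a ballet dance training course". Section 11.2 has each participant perform "3 trials of 30 seconds while standing on a Wii board" in each stance condition, and the documents do not say how the three trials are combined.

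**The concern.** The wording puts the absolute value outside the average. If the averaged quantity is already unsigned, the absolute value does nothing, so its presence suggests that per-axis velocity was averaged with its sign. Movements in opposite directions then cancel, and only the distance between the first and last CoP positions is left. A participant could sway widely, finish near the starting point and score close to zero. Two outcomes meant to test reduced sway would then say little about it.

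Displacement is open in a similar way. It could be net shift, range, root-mean-square excursion or path length. Net shift has the same weakness. Path length would make displacement and unsigned speed the same outcome in different units, so a reader could count one result as two.

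**Working it through.** The plan states no figure on this point to reproduce. The check has four steps.

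**1. What signed averaging would give.** Inputs: trial time T = 30 s (sections 11.2 and 11.3) and CoP position x along one axis. The mean signed velocity is the sum of successive differences divided by T. The sum telescopes:

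mean v = [Σ (x(i+1) − x(i))] / T = (x_end − x_start) / 30 s.

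Its absolute value is |x_end − x_start| / 30 s. Simulated traces agreed with this to rounding error (about 1e-15). As an example, take a sway of amplitude 5 mm at 0.3 Hz. Over 30 s it makes 0.3 × 30 = 9 whole cycles and ends where it began, so the signed measure is 0. The unsigned measure is 4 × 5 mm × 0.3 per s = 6.0 mm/s.

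**2. How many tests depend on the reading.** There are 5 measures × 2 conditions = 10 between-group tests: 4 on speed, 4 on displacement and 2 on area.

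| Speed | Displacement | Consequence |
|---|---|---|
| unsigned | range or root-mean-square | none |
| unsigned | path length | 4 tests repeat another 4 |
| unsigned | net shift | 4 displacement tests weak |
| signed | range, root-mean-square or path length | 4 speed tests weak |
| signed | net shift | 8 tests weak |

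In the last row the speed tests repeat the displacement tests only if displacement is also taken as an absolute value; section 11.3 attaches that term to speed alone. Exact repetition in either row also needs every trial to run the full 30 s, and section 11.2 lets participants stop at any moment. Where both conditions hold, dividing by 30 leaves ranks unchanged: in simulated data the Mann-Whitney p-values were identical before and after division (0.218 and 0.218; 0.323 and 0.323). Area is no better defined than the other measures, so the table does not show it to be safe.

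**3. How weak the signed measure would be.** The documents give no variances, sampling rate or noise level, so these figures are illustrative. They assume 30 s traces with sway frequencies of 0.05–1.5 Hz, a median sway SD of 4 mm and a between-person log-SD of 0.3. Rank correlation with true sway amplitude:

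- |mean velocity|: 0.29–0.33 for one trial, about 0.50–0.57 for the mean of three.
- Mean absolute velocity, no noise: 0.945–0.966 for one trial, 0.98–0.99 for the mean of three.
- Mean absolute velocity, one trial, assumed 0.5 mm noise: 0.54–0.94 at 40 Hz and 0.17–0.81 at 100 Hz unfiltered; 0.91–0.96 with a 10 Hz low-pass filter.

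**4. Whether the two readings could be confused in the data.** For a stationary trace with start and end independent, the mean of |x_end − x_start| is 2·SD/√π. With an assumed SD of 3 mm this is 3.39 mm, or 3.39/30 = 0.11 mm/s. With 5 mm it is 5.64 mm, or 5.64/30 = 0.19 mm/s. Simulated mean-reverting traces with these SDs gave about 0.11–0.19 mm/s signed and about 7–79 mm/s unsigned at assumed rates of 10–100 Hz, a ratio of about 65 to 430. The two readings differ so much in size that the stored values would show which one was used.

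**The case for a change.** The strongest case for acting is that clarification is cheap and the possible loss is not small. The algebra needs no assumption about sway, no other section supplies a definition, and in the worst reading 8 of 10 between-group tests would be misread as sway. The study also continues over semesters: "their postural stability will be assessed at the beginning and end of the semester", and after Spring 2019 the lead for data collection may "find another Skidmore student to help with data collection who is trained with this protocol". A speed summed from successive samples depends on sampling rate and filter, so an unwritten formula might drift.

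The algebra stands, and so does the observation that the definitions are incomplete. The step from there to a fault in the plan does not. The only evidence for signed averaging is one redundant phrase attached to a word that already means an unsigned quantity. Loose wording for mean absolute velocity explains it equally well.

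The point about settings shows no fault either. No section says that settings differed between sessions, and section 11.2 describes a calibrated system run by testers who must first demonstrate competency. The noise figures that make the sampling rate look decisive are assumed.

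**Conclusion.** The concern is a fair question about wording, but it does not call for a change to the plan. Read in its ordinary sense, the text leads an analyst to mean absolute velocity per axis, which follows sway closely (0.945–0.966 in the noise-free illustration). The harmful reading would affect 4 or 8 of 10 between-group tests, but it requires an error that the documents do not show. Even then, the single-trial correlation of about 0.3 overstates the loss if three trials are averaged (about 0.5).

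The section describes work in the past tense, so rewording it would not alter what was computed for those data. Naming the formulas for speed, displacement and area is ordinary reporting detail. If signed averages had been used, their very small size should reveal it. This conclusion rests on the ordinary meaning of speed and on the absence of contrary evidence. The correlations and sizes rest on assumed traces and are illustrative; the identity in step 1 is exact for a full 30 s trial.
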